## 11. Direct Access to Source Data/Documents

The Sponsor-Investigator, Dexcom, and the study doctor/site will permit any program-related monitoring, audits, IRB/IEC review, and regulatory inspection(s), deemed necessary by the IRB, and will provide direct access to relevant source data/documents as may be required.

## 12. Risks

This is a minimal risk study. Program participants are being asked to wear a Fitbit activity tracker and a Dexcom CGM system.

### Risks of the Activity Tracker Device

The Fitbit has a wrist band. Skin irritation from these devices is a remote possibility (there are very few reports in the online literature regarding this occurrence with similar devices). Study participants who experience skin irritation will be instructed to remove the activity tracker during sleep, and/or to alternate wearing it on the opposite wrist. There is also a slight risk that the privacy of the activity tracker data could be exposed if an unauthorized source hacks into the activity tracker's data system. Due to security and authorization that Savvysherpa has in place this risk is minimal.

## Risks of CGM

When the wire-like sensor is deployed by the applicator, participants can expect a sensation similar to a needle insertion for a blood draw. Risks of CGM use include discomfort during sensor insertion, along with pain, inflammation, redness, swelling, minor bleeding and minor infection at the sensor insertion site. Participants might also experience these symptoms as a result of contact between the adhesive pad of the sensor and the skin. In rare cases, an infection can spread to other parts of the body.

Allergic reactions can develop in response to the sensor, the adhesive, and other parts of the CGM. If these symptoms occur, participants have the ability to remove the CGM at will and can anticipate that their symptoms will clear up within one week.

The sensor and/or applicator may fracture during use. If a sensor remains in the skin, there is minimal risk to the patient as long as a physician confirms there are no symptoms of infection or inflammation.

Patients will be advised that the investigational sensor, transmitter, and smartphone must be removed before Magnetic Resonance Imaging (MRI), Computed Tomography (CT) scan, or diathermy treatment. The device is MR Unsafe. Participants should not bring any portion of the device into the MR environment. The Dexcom IUO CGM System has not been tested during MRI or CT scans or with diathermy treatment. The magnetic fields and heat could damage the device, causing it to stop displaying glucose readings, display inaccurate glucose readings, or prevent alerts.

Patients will also be advised of CGM system warnings that may affect the proper operation of the device and/or the patient's safety. These warnings will be described in the informed consent and authorization form, and in the informational materials provided to patients when they receive their systems.

Patients will be provided with a phone number for Dexcom Customer Care and Technical Support that has been set up exclusively for patients participating in this study. Staff for this line will be well-qualified to address any potential questions and risks associated with the investigational device. Significant or serious health risks with CGM are not anticipated.

The same precautions have been taken to code and/or encrypt the investigational system's electronic data as have been taken with the commercial Dexcom devices. Regardless, throughout the program, patients will be advised not to rely on the device to make any treatment decisions, and to measure their blood glucose in order to confirm any symptoms of hypoglycemia.

## Risks of Glucose Meter

Finger-stick blood samples will be taken during this study. This may cause some discomfort, pain, bruising, and/or soreness afterwards. Rarely, an infection may occur. Routine finger-stick sampling for use with a blood glucose meter is already standard-of-care for T2D patients.

## Risks of Medical Record Review and Data Collection

This project involves extracting Protected Health Information (PHI) from patients' medical records. PHI will also be extracted from Dexcom patient databases. Activity tracker data will be synced via https from the trackers to the secure servers of Fitbit. Data collected from the activity trackers will then be sent via https to Savvysherpa's secure servers. Personally Identifiable Information (PII) will be collected from health providers, Dexcom, and/or Fitbit, as well as through survey responses, coach-patient texts, call recordings, online program engagement, and/or in-person group participation at educational classes.

The combined dataset will be de-identified by removing personal identifiers from each system and replacing them with a unique study identifier.

The combined data set will be stored in Savvyshera's HITRUST-certified secure server environment that can only be accessed by authorized personnel via a physically secured room. Any links between personal identifiers from the source systems and study identifier will be deleted ten years after study completion. Recordings of educational classes, coaching sessions, and coach-patient texts will also be deleted ten years after study completion. PII associated with these recordings may be visible to program staff and Dexcom in the course of quality improvement efforts and the development of training, but the identities and privacy of participants will otherwise be maintained.

There is a risk that the information could be inadvertently disclosed to another entity although the risk is very small given the data security measures in place.

#### Risks of Unsecured Communication

Participants will be contacted via phone and secure text messaging. Phone communication will not be secured putting the participants at risk of having PII inadvertently disclosed. Secure text messaging is subject to hacking.

### 13. Benefits

Participants in the study may develop a greater personal understanding of how their lifestyle habits (e.g. physical activity, diet) affect their glucose levels (e.g. average glucose, PPG, GV, and NG). What they learn will help them understand better how to self-manage their glucose and be healthier. Information gained from this program will be used to further refine the program so that it can benefit more people.

### 14. Compensation

During the study, participants will use a Dexcom CGM system for 10 weeks at no-cost to them. Study participants will also have access to their personal CGM data (up to 24 hours) via the Dexcom CGM system app while using the CGM system. Upon request and after they have finished using the system, participants will receive a summary report of their CGM data. Participants will receive free over-the-phone and secure text messaging communication with coaches related to CGM and diabetes self-management.

Participants who wear their CGM systems for 10 weeks and continue to wear and upload data from their activity trackers (defined as syncing at least every three weeks through February 28, 2018) may keep the activity tracker (\$150 Fitbit Charge 2) and smartphone without a data plan (\$200). In addition, patients who received a glucometer (\$40) may keep it.

Study participants will also continue to have access to their personal physical activity dashboard after the study ends.

As compensation for patients' time/travel associated with providing certain data, patients will receive payment as follows:

- Patients will receive \$40 for their initial A1C test at the beginning of the study; \$20 for an A1C at 90 days; and \$20 for an A1C at 180 days.

- Patients on basal insulin who report their daily insulin dose will receive \$0.50 for each day they provide this data.
- Following the CGM program, patients who provide their fasting fingerstick blood glucose measures will receive \$0.50 per day for each day they provide data.

## 15. Quality Control and Quality Assurance

All study staff interacting with patients will receive training in the fundamentals of the ethical treatment and safety of human subjects. The Principle Investigator will be responsible for assuring that program staff receive this training and that the entire research team adheres to the protocol. The Principle Investigator will also ensure that the principles of Good Clinical Practice are being followed.

In addition, the research team participating in this study represent individuals whose qualifications and experience have equipped them to collect and analyze confidential patient data. The study's medical advisors (Co-Investigators), study doctor, and on-site clinical research coordinator will meet with the Principle Investigator to review progress and offer any direction that may be needed with regard to patient safety. The HITRUST-certified environment in which data will be stored will provide a high level of protection for all data collected (see below).

## 16. Ethics

The proposed program will involve patients with a medical condition. Patients will only be invited to the program when their physicians have agreed that the program should be offered to them. The program recruitment strategies assure that prospective patients have access to a staff member with whom they can discuss and ask questions about the program before signing an informed consent form and then while participating in the program. Patients will have an opportunity to review program materials and ask questions of research staff before signing and dating the informed consent form. There is no limit to the number of times patients may speak with program staff before making a decision about whether to participate.

As some participants may not want their condition to be known to others, they will have the option and resources to start using the CGM system without having to attend a group visit. The program will serve as an adjunct to normal medical care.

Patients will have the freedom to use the CGM system and activity tracker at times of their choosing. They will be participating at-will, may withdraw from the study any time, and will face no adverse consequences from the program or their providers if they withdraw from the study or choose not to participate at all.

We want this study to be minimal risk. As such not all patients with T2D will be eligible. The inclusion/exclusion criteria preclude certain patient populations with T2D that would benefit from participating in the study. However, resource constraints and the management of risk do not allow for all patients with T2D to participate at this time.

## 17. Data Handling and Record Keeping

Data will be collected by these entities:

- Savvysherpa will collect medical record data and claims cost data from participants' medical records.
- Dexcom will collect interstitial glucose data and data related to device use (such as calibration timestamps) from participants in the CGM program.
- Savvysherpa will collect program data from the participants directly and from the program. Program data will include survey responses, call recordings, coach-patient secure texts, and/or in-person group participation at educational classes.
- Fitbit will collect data from activity trackers.

Dexcom, Fitbit, and provider data will be shared with Savvysherpa. Savvysherpa will have access to versions of the data that include personally identifiable information (PII) and protected health information (PHI) from all of these entities.

PHI will be extracted from the following sources and brought into Savvysherpa's study infrastructure—a HITRUST-certified secure server environment.

- Savvysherpa will work with providers to assure secure data transfer of medical record and claims cost data.
- Claim records and medical records stored in a physically secured room will be accessed by an authorized party, extracted from the room using documented procedures, and loaded into the study infrastructure.
- Dexcom CGM patient readings will be sent from Dexcom secure servers over a secure, encrypted connection to the secure, encrypted study cloud infrastructure.
- Data from the activity trackers will be synced via Bluetooth to the client's application. From the application, the data will be sent via https to the client's secure servers. From the client's secure servers, the data will be sent to Savvysherpa via https.
- Authorized program advisors will communicate with patients via phone call, and also by secure text messaging to smartphones issued to each patient. Messages will be delivered to an app utilizing patient's credentials over an encrypted connection to the messaging server. Data, notes, and recordings related to these transactions will be stored within the study infrastructure.

Within the study infrastructure, communication between servers and data stored on servers will be encrypted and accessed via login by authorized personnel for the purpose of assisting and advising patients in the program, and for conducting related analysis and program optimization.

The combined dataset will be de-identified by removing personal identifiers from each system and replacing them with a unique study identifier. A list connecting personal identifiers and the unique identifier will be maintained and stored by Savvysherpa in a separate password-protected database. Any links between personal identifiers from the source systems and study identifier will be deleted 10 years after the completion of the study. Recordings of coaching sessions and group participation activity will also be deleted 10 years after the completion of the study.

Over the course of the program Savvysherpa will have the PII necessary to allow for patient contact as outlined in the protocol. This will be described in the informed consent document.

## 18. Financing and Insurance

The Sponsor of the study is Savvysherpa, Inc. and its fully-owned subsidiary SavvySugars, LLC. Some or all funding for this program will be provided by Savvysherpa and/or its affiliates.

## 19. Publication Policy

The investigators intend to publish on the proposed implementation activities or results.

## 21. Appendix A

### Piloting the Dexcom CGM System with Medicare Type 2 Patients: Phase 1

September 2016

#### **Executive Summary**

As part of a health system's diabetes quality improvement initiative, we created an educational program for Medicare patients with type 2 diabetes incorporating the Dexcom G5 continuous glucose monitoring (CGM) system and activity trackers. In this initial two-week pilot program, we wanted to learn about patients' recruitment rates, compliance with device tasks, and general responses to the CGM system and program model.

#### **Recruitment**

- We called 60 patients to invite them to the program, reaching 39 (65%) of patients by phone.
- 16 (27%) accepted the phone invitation.
- 11 (18%) participated by attending the in-service and applying their first CGM sensor.

#### **Compliance**

- In week one, 10 out of 11 participants independently calibrated their first CGM sensor after the sensor's two-hour warm-up period.
- In week two, 8 out of 11 participants independently applied and calibrated their second CGM sensor after the sensor's two-hour warm-up period.

#### **General responses**

- Participants joined the program primarily because of their physicians' recommendations.
- Participants either 1) quickly understood the potential for using CGM to identify behaviors that impact their glucose, or 2) did not demonstrate an understanding of this relationship and would need more support to do so.
- Many participants struggled with the small-motor skills needed to apply the CGM sensor and transmitter and to press buttons on the receiver and activity tracker.
- Roughly half of participants were interested in using the CGM system again to manage their diabetes.

#### **Conclusions**

Based on these findings, we conclude that:

- A portion of this population will wear a CGM device and can, with training, remove and apply CGM sensors by themselves.
- With support for their individual needs, this population can benefit from using CGM to understand and manage diabetes.
- Participants need more time and coaching to use CGM devices confidently and to understand their data.
- Sharing patients' data with program staff would allow the program to design and provide relevant support for those patients.

#### **Recommendations**

To continue to develop this program, we recommend:

- Phase 2: Implement and observe other methods of delivering devices, educating patients, and obtaining patients' CGM data.
- Phase 3: Based on findings from phases 1 and 2, design and test this program on a larger scale with the goal of improving patients' A1c levels.

## 22. Appendix B

### Adverse Events Severity and Relatedness Questions

May 2017

When patients share a complaint, program coaches will identify the complaint in the Anticipated Complaints Guidebook. Based on the complaint type, coaches will then ask questions to determine:

1. Severity of the complaint (e.g., Mild, Moderate, or Severe), and
2. Relatedness of the complaint to the use of program devices (e.g., Not Related, Probably Not Related, Possibly Related, and Probably Related)

Coaches will document answers in the templates provided, including the Adverse Event document.

If the complaint falls in any of the severity categories highlighted in red, the coach will make a “warm transfer” to the study doctor and/or his staff so that the patient can be scheduled for an ancillary appointment.

If the complaint is an emergency, patients will be instructed to call 911.

If a patient has a complaint that is not listed in the Anticipated Complaints Guidebook, the coach can “warm transfer” the patient to the study clinic for guidance. The coach will document as much as possible in Adverse Event document. Follow up with the clinic will determine severity and relatedness.

Coaches will contact the PI when situations arise that are not covered in the Anticipated Complaints Guidebook.

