- There are no expected electrical safety risks as the device has passed the electrical safety tests as per EN45502-1 and EN60601;

- If the subject feels any discomfort during the course of the study, he/she will be able to remove the device immediately (the device is not permanent);
- The device is being used to complement, not replace, self-monitoring of blood glucose meter information, and readings are not intended to be used alone to make diabetes self-management decisions. As with the currently approved device and per intended use of similar technologies, subjects in the study will be instructed not to use the device for diabetes therapy or management;
- Subjects will be instructed to monitor their blood glucose levels as per their usual practice.

Adverse events (AE) associated with the use of the device include pruritus (severe itchiness present 48 hours after removal), erythema (reddening of the skin present 48 hours after removal), and inflammation (swelling and pain, defined as 8 or greater on a 10 point scale 48 hours after removal) where the adhesive touches the skin; local infection at insertion site; and shooting pain located at the site of the sensor (defined as 8 or greater on a 10 point scale). Rarely, the sensor wire will fracture when the sensor is being inserted, worn, or removed. If a sensor breaks and no portion of it is visible above the skin, the participant will be instructed to not remove it and seek medical care from the study doctor and/or his staff.

No serious adverse events (SAE) are expected as a result of participation in this minimal risk study. However, AE and SAE will be monitored in the following ways:

- Participants in the study will be instructed to call the study doctor's clinical research coordinator to report all AE and SAE related to the use of the study devices. The study doctor and/or his staff will assess the severity of any health problems associated with the device, and if needed, see the patient at the study clinic to assure appropriate care.
- Study coaches will listen for any reports of AE or SAE in the course of their communications with participants, and will connect reporting patients with the study doctor's clinical research coordinator so events can be assessed and documented and patients can receive care, if needed.

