#### Skin Redness or Rash – Severity Category

1. On a scale of 1 to 10, where 1 is very little, and 10 is severe, how would you rate the redness of your skin or rash?
  - If 1-5, do not record as AE, **unless itchiness and/or pain are moderate**
  - If 6-7, Mild AE
  - If 8-9, Moderate AE**
  - If 10, Severe AE**
2. Are you experiencing **pain or itchiness** where your skin is red or where you have a rash?
  - If no, stop.
  - If yes, on a scale of 1 to 10 where 1 is very little, and 10 is severe, how would you rate the **itchiness**?
    - If 1-5, do not record as AE
    - If 6-7, Mild AE
    - If 8-9, Moderate AE**
    - If 10, Severe AE**

- If yes, on a scale of 1 to 10 where 1 is very little, and 10 is severe, how would you rate the **pain**?
  - If 1-2, do not record as AE
  - If 3-5, Mild AE
  - If 6-8, Moderate AE**
  - If 9-10, Severe AE**

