#### **Skin Itchiness – Severity Category**

1. On a scale of 1 to 10, where 1 is very little, and 10 is severe, how would you rate your skin itchiness?
  - If 1-5, do not record as AE
  - If 6-7, Mild AE
  - If 8-9, Moderate AE
  - If 10, Severe AE**

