### Insertion Site Swelling – Severity Category

1. On a scale of 1 to 10, where 1 is very little, and 10 is severe, how would you rate the amount of swelling?
  - If 1-5, do not record as AE
  - If 6-7, Mild AE
  - If 8-9, Moderate AE
  - If 10, Severe AE

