### **Insertion Site Infection – Severity Category**

1. Do you notice signs of infection that include inflammation, drainage, pus discharge and pain?
  - a. If no, then stop
  - b. If yes, on a scale of 1 to 10, where 1 is very little and 10 is severe, how much inflammation, drainage, pus discharge and pain do you have?
    - If 1 – 8, **Moderate AE**
    - If 9 – 10, **Severe AE**

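### Appendix B's itch, pain, swelling and bruising questions do not probe other signs, so one sensor site can go unrecorded under one complaint type and be Moderate under another

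*Protocol*

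**What the plan says.** Appendix B opens with the sorting step: "When patients share a complaint, program coaches will identify the complaint in the Anticipated Complaints Guidebook". The next step follows from it: "Based on the complaint type, coaches will then ask questions to determine" severity and relatedness. A separate set of severity questions is then printed for each complaint.

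- **Redness or rash.** A low redness score has an exception: "If 1-5, do not record as AE, unless itchiness and/or pain are moderate". The coach then asks about pain and itch "where your skin is red or where you have a rash".
- **Itch.** One severity question: "how would you rate your skin itchiness". Scores 1-5 are not recorded, without exception.
- **Swelling.** One severity question: "how would you rate the amount of swelling". Scores 1-5 are not recorded, without exception.
- **Insertion site pain.** One severity question, on how far the pain affects daily activities. Scores 1-2 are not recorded.
- **Bruising.** A severity score, then whether the bruise or bump is growing. Scores 1-5 without growth are not recorded.
- **Infection.** A gate question, "Do you notice signs of infection that include inflammation, drainage, pus discharge and pain", and then a rating. Ratings 1-8 are Moderate and 9-10 Severe.

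Section 9 (Assessment of Safety) lists the device AEs separately. Inflammation is described there as swelling together with pain, with a criterion of 8 or more on a 10-point scale 48 hours after removal. The entry "local infection at insertion site" carries no threshold.

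**The concern.** The cross-check in the redness set shows that its authors saw how one sign can understate a site reaction. It was not carried over to the neighbouring sets. AE status and grade can therefore depend on which complaint is entered first when the patient does not mention the other signs.

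Two AEs listed in Section 9 are exposed. Inflammation needs both swelling and pain, but the swelling questions never ask about pain, so they cannot establish it on their own. Local infection counts at any severity, but signs of drainage or pus are asked about only once the complaint has been classified as infection.

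The counts matter because Section 3 describes the CGM system as not approved by the FDA, and Section 9 sends AE information to the IRB, the manufacturer and the FDA. Ten weeks of wear with 10-day sensors means 70 / 10 = 7 sensors per participant, so site complaints can arise repeatedly.

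**Working it through.** The plan states no figure for this point, so there is none to reproduce. The check applies Appendix B's printed score bands to the same site under different entry complaints.

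| Entry complaint | Not recorded | Mild | Moderate | Severe | Other signs asked about |
|---|---|---|---|---|---|
| Redness or rash | 1-5, with exception | 6-7 | 8-9 | 10 | Itch, pain |
| Itch | 1-5 | 6-7 | 8-9 | 10 | None |
| Swelling | 1-5 | 6-7 | 8-9 | 10 | None |
| Site pain | 1-2 | 3-5 | 6-8 | 9-10 | None |
| Bruising | 1-5, unless growing | 6-7 | 8-9 | 10 | Growth only |
| Infection, signs present | None | None | 1-8 | 9-10 | Inflammation, drainage, pus and pain in the gate question |

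**One site.** Take redness 5, itch 5, swelling 5, pain 8, and signs of infection rated 8. The patient names one sign and volunteers nothing else.

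- Entered as itch: 5 is in 1-5, so not recorded.
- Entered as swelling: 5 is in 1-5, so not recorded.
- Entered as redness: redness 5 alone would not be recorded, but the pain follow-up gives 8, in 6-8, so Moderate.
- Entered as site pain: 8 is in 6-8, so Moderate.
- Entered as infection: 8 is in 1-8, so Moderate.

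**Swelling (or itch) against pain.** There are 10 x 10 = 100 score pairs.

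- Unrecorded under swelling or itch (5 scores) but recorded under pain (3-10, 8 scores): 5 x 8 = 40.
- Of these, Moderate or Severe under pain (6-10, 5 scores): 5 x 5 = 25.
- Of the 40, pain at 8 or more, the level Section 9 uses (8-10, 3 scores): 5 x 3 = 15.

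**Swelling (or itch) against infection rating, signs present.** Unrecorded under swelling or itch but Moderate or Severe under infection: 5 x 10 = 50 of 100.

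**Pain against infection rating, signs present.** Unrecorded under pain (1-2) but Moderate or Severe under infection: 2 x 10 = 20 of 100.

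**Redness.** This set also lacks the infection question. Redness 5, itch 5 and pain 2 at a site with discharge is not recorded under redness, but is at least Moderate if entered as infection.

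All of these count rule combinations and say nothing about how often each occurs. The comparison also treats a pain score as the same number in both places, although the redness set rates the pain itself and the pain set rates its effect on daily activities.

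**The case against.** The strongest reply is that the printed questions are only part of the system.

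1. **Classification.** The coach classifies the complaint, using a Guidebook that is not at hand. Section 9 also cites an Appendix D with AE guidance for coaches, which is not in the available text. Either could contain cross-prompts. This stands. A reader might infer that the patient's choice of word alone fixes the outcome, but the protocol does not say so.
2. **More than one question set.** Nothing limits the coach to a single set. A patient who mentions swelling, pain and discharge has several listed complaints. This also stands, and it confines the gap to signs the patient does not volunteer.
3. **Other routes.** Section 6 (Integration with patient care) and Section 9 direct patients to the research coordinator, who assesses severity and relatedness. Coaches connect patients who report events with the coordinator, and the manufacturer's support line forwards reports. These routes limit the gap but do not close it. For a listed complaint, Appendix B ties the transfer to the severity category reached, so a low swelling score triggers none. Its open fallback covers only complaints missing from the Guidebook. The sections leave unclear whether every site complaint reaches the coordinator.
4. **Section 9 thresholds.** Pain of 3-7 falls below Section 9's criterion of 8, so many unrecorded pairs would not be AEs there either. This is right for 40 - 15 = 25 of the 40 pairs. The other 15 reach the criterion on pain, although the text does not settle whether swelling must also reach 8. The reply does not touch infection, which has no threshold.
5. **Purpose.** The study is formative and AE rates are not among its named effectiveness endpoints. That lowers the stakes for inference, but the safety reporting duties in Section 9 remain.

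**Conclusion.** The point holds as a gap in the printed questions. When other signs are not volunteered, the same site can be unrecorded under swelling or itch (scores 1-5) and Moderate or worse under redness, pain or infection. The swelling questions cannot by themselves establish Section 9's inflammation, and local infection can go unasked under all five of the other skin and site entries examined.

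The size can be stated only as rule combinations: 40 of 100 swelling-by-pain pairs discordant, 25 of them Moderate or Severe under pain, and 50 of 100 swelling-by-infection pairs.

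A reader might go further and assume independent scores, uniform on 1-10. The redness questions would then record 1 - 0.5 x 0.5 x 0.2 = 95% of reactions, against 50% for itch or swelling. The documents do not support this. They give no score distribution, signs at one inflamed site are unlikely to be independent, and the sign a patient names is probably related to which is worst. The 95% also counts Mild itch or pain, whereas the redness exception refers to moderate; on that reading it is 1 - 0.5 x 0.7 x 0.5 = 82.5%. Multiplying by seven sensors would multiply an unknown probability.

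The conclusion rests on Appendix B as printed. Cross-prompts in the Guidebook or Appendix D would narrow or remove the gap. The change is worth making because it is cheap and sets no new threshold.

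**What to change.** For any skin or insertion-site complaint, have the coach also ask the existing redness, itch, pain and swelling questions and the infection gate question, whichever sign was named first. Bruising keeps its own questions as well. Leave all cut-points as they are.

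Record each sign under its own AE type and grade. Merging them into one site reaction at the highest grade would lose the types that Section 9 lists separately, including the infection count. Use the highest grade only to decide whether Appendix B's existing transfer rule applies.

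Two passages also need reconciling by the sponsor: the Appendix B score bands with the Section 9 AE definitions (level and 48-hour timing), and the grade-dependent transfer in Appendix B with the statements in Sections 6 and 9 that reported events go to the coordinator. If the Guidebook or Appendix D already contains cross-prompts, Appendix B should say so.

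The cost is a revised script, slightly longer complaint calls and somewhat higher recorded AE counts.
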